4.1. Test Schedule For Hepatic Safety Monitoring And Follow Up After Discontinuing Imetelstat

For patients who experienced any treatment emergent abnormality in LFTs, defined as any grade abnormality in patients with normal value at baseline or any higher grade shift from baseline in patients with an abnormal baseline, or value more than 2x baseline if baseline was Grade ≥ 3 , or hepatic adverse events present at imetelstat discontinuation, obtain follow-up as defined in [Table 4](#) below until resolution to at least baseline grade or, less than 2x baseline value if baseline was Grade ≥ 3 for at least 2 consecutive determinations.

Table 4: Test Schedule for Hepatic Safety Monitoring And Follow Up After Discontinuing Imetelstat

Assessment 1	Post-Study Completion/ Early Treatment Termination Visit ¹ (Monthly ± 7 Days)
Serum chemistry ²	X
CBC; a concurrent reticulocyte count, and peripheral smear (to assess for hemolysis) and a concurrent haptoglobin and fasting bile acids ³	X ³
Record adverse events ⁴	X
Record concomitant medications	X
Record additional assessments/evaluations ⁵	If performed
Doppler ultrasound of abdomen (optional) ⁶	Once

CBC = complete blood count; ET = essential thrombocythemia; PV = polycythemia vera.

¹ Monthly follow up post-study completion/early treatment termination until resolution criteria are met.

² Serum chemistries include ALT, AST, ALP, total & direct bilirubin, GGT, BUN, creatinine, and serum ferritin.

³ Perform only if total bilirubin is elevated. CBC includes white cell count (WBC) count; absolute neutrophil count (ANC); hemoglobin; and platelet count.

⁴ Continue to collect adverse events and serious adverse events regardless of attribution until resolution of liver biochemistry or hepatic adverse events.

⁵ Record any additional clinical evaluations that are performed based on clinical decisions to evaluate new onset or ongoing liver function abnormalities, or clinical findings. Includes physical examination, laboratory tests, radiographic or other diagnostic studies that are performed to evaluate new onset or ongoing liver function abnormalities, or clinical findings.

⁶ Performed once at any time during hepatic safety monitoring/follow-up after imetelstat discontinuation, in patients who had baseline ultrasound performed, unless post baseline assessment previously performed before entering hepatic safety follow-up period. The ultrasound will assess status of hepatobiliary architecture, which includes detection of any gross liver abnormalities; results will be compared to the baseline scan.

5. GROUPING FACTORS

All study arms (A, B, C, D, E, F, and G) are now permanently closed to enrollment.

6. REGISTRATION/RANDOMIZATION PROCEDURES

6.1. Registration Procedures

1. To register a patient, access the Mayo Clinic Cancer Center (MCCC) web page and enter the registration/randomization application. The registration/randomization application is available 24 hours a day, 7 days a week. Back up and/or system support contact information is available on the Web site. If unable to access the Web site, call the MCCC Registration Office at [REDACTED] between the hours of 8 a.m. and 4:30 p.m. Central Time (Monday through Friday).

The instructions for the registration/randomization application are available on the MCCC web page (<http://hsrwww.mayo.edu/ccs/training>) and detail the process for completing and confirming patient registration. Prior to initiation of protocol treatment, this process must be completed in its entirety and a MCCC subject ID number must be available as noted in the instructions. It is the responsibility of the individual registering the patient to confirm the process has been successfully completed prior to release of the study agent. Patient registration via the registration/randomization application can be confirmed in any of the following ways:

- Contact the MCCC Registration Office [REDACTED] If the patient was fully registered, the MCCC Registration Office staff can access the information from the centralized database and confirm the registration.
- Refer to “Instructions for Remote Registration” in section “Finding/Displaying Information about A Registered Subject.”

2. Documentation of IRB approval must be on file in the Registration Office before an investigator may register any patients.

In addition to submitting initial IRB approval documents, ongoing IRB approval documentation must be on file (no less than annually) at the Registration Office (fax: [REDACTED]). If the necessary documentation is not submitted in advance of attempting patient registration, the registration will not be accepted and the patient may not be enrolled in the protocol until the situation is resolved.

When the study has been permanently closed to patient enrollment, submission of annual IRB approvals to the Registration Office is no longer necessary.

3. Prior to accepting the registration, the registration/randomization application will verify the following:
 - IRB approval at the registering institution
 - Patient eligibility
 - Existence of a signed consent form
 - Existence of a signed authorization for use and disclosure of protected health information (U.S.A. institutions only) [delete parenthetical expression (only) when not applicable, i.e. no non-USA participants]
4. Treatment on this protocol must commence at Mayo Clinic Rochester under the supervision of a hematologist.
5. Treatment cannot begin prior to registration and must begin \leq 7 days after registration.
6. Pretreatment tests/procedures (see Section 4) must be completed within the guidelines specified on the test schedule.
7. All required baseline symptoms (see Section 10.6) must be documented and graded.
8. Study drug is available on site.

7. PROTOCOL TREATMENT

7.1. Treatment Schedule

7.1.1. Imetelstat Treatment

This is a single center, open-label study of imetelstat in patients with Intermediate-2 or high risk PMF/post-ET/PV MF (Arms A, B, C, E and F) or blast-phase MF (Arm D only) or spliceosome-mutated (or with ring sideroblasts) MDS/MPN (Arm G only).

Imetelstat will be administered as a 2-hour IV infusion (\pm 10 minutes). The current weight will be used to calculate the dose of imetelstat. All patients must be premedicated prior to imetelstat administration.

As of 22 January 2014, all arms are permanently closed to accrual.

7.1.1.1. Arm A Treatment Schedule

(Arm A permanently closed to accrual)

Agent	Dose	Route	Day	Cycle (ReRx) ± 3 days ¹
Imetelstat	9.4 mg/kg	IV as 2 hour infusion	1 ^{2,3}	Every 21 days

¹ Patients may continue to receive imetelstat study treatment for as long as they derive clinical benefit or until study end. The study will end when all subjects have discontinued study drug, the last patient enrolled has been treated for 5 years, or imetelstat is commercially available in the United States, whichever occurs first.

² If the patient has not achieved a CR or PR, by the end of Cycle 6, the dosing frequency may be increased to up to weekly using the **current dose level** at the discretion of the Investigator. The patient must be tolerating the current dose level without significant toxicity. Increase in dosing frequency is only allowed after Cycle 6. The cycle length will be 21-28 days. If the dosing frequency is increased to once weekly, the cycle length will remain 21 days. If the dosing frequency is increased to once every 2 weeks, the cycle length will be 28 days.

³ For patients whose response has plateaued for a minimum of 3 months, the dosing frequency may be reduced after Cycle 6 and the cycle length will be the length of the dosing interval. For example, if the dosing frequency is decreased to once every 3 months, the cycle length will be 84 days. Dosing can also be interrupted until relapse and restarted, in such patients, per physician discretion. In the case of interruption, a cycle will be 3 months while treatment is held and the patient will restart at the dose level/schedule they were receiving at the time of interruption.

7.1.1.2. Arm B Treatment Schedule

(Arm B permanently closed to accrual)

Induction: Cycle 1				
Agent	Dose	Route	Day	Cycle (ReRx) ± 3 days
Imetelstat	9.4 mg/kg	IV as 2 hour infusion	1, 8, 15	Cycle 1 is 21 days
Maintenance: Cycles 2 and beyond ¹				
Agent	Dose	Route	Day	Cycle (ReRx) ± 3 days
Imetelstat	9.4 mg/kg	IV as 2 hour infusion	1 ^{2,3}	Every 21 days (Cycles 2 and beyond)

¹ Patients may continue to receive imetelstat study treatment for as long as they derive clinical benefit or until study end. The study will end when all subjects have discontinued study drug, the last patient enrolled has been treated for 5 years, or imetelstat is commercially available in the United States, whichever occurs first.

² If the patient has not achieved a CR or PR, by the end of Cycle 6, the dosing frequency may be increased to up to weekly using the **current dose level** at the discretion of the Investigator. The patient must be tolerating the current dose level without significant toxicity. Increase in dosing frequency is only allowed after Cycle 6. The cycle length will be 21-28 days. If the dosing frequency is increased to once weekly, the cycle length will remain 21 days. If the dosing frequency is increased to once every 2 weeks, the cycle length will be 28 days.

³ For patients whose response has plateaued for a minimum of 3 months, the dosing frequency may be reduced after Cycle 6 and the cycle length will be the length of the dosing interval. For example, if the dosing frequency is decreased to once every 3 months, the cycle length will be 84 days. Dosing can also be interrupted until relapse and restarted, in such patients, per physician discretion. In the case of interruption, a cycle will be 3 months while treatment is held and the patient will restart at the dose level/schedule they were receiving at the time of interruption.

7.1.1.3. Arms C and D Treatment Schedule

(Arms C and D permanently closed to accrual)

Agent	Dose	Route	Day	Cycle (ReRx) ± 3 days ¹
Imetelstat	9.4 mg/kg	IV as 2 hour infusion	1, 8, 15, 22 ²	Every 28 days

¹ Patients may continue to receive imetelstat study treatment for as long as they derive clinical benefit or until study end. The study will end when all subjects have discontinued study drug, the last patient enrolled has been treated for 5 years, or imetelstat is commercially available in the United States, whichever occurs first.

² For patients without response after the first two cycles, dosing might be increased to either Days 1, 3, 5 or Days 1, 3 every 2 to 4 weeks, per physician discretion. For patients whose response has plateaued for a minimum of 3 months, the dosing frequency may be reduced after Cycle 6 and the cycle length will be the length of the dosing interval. For example, if the dosing frequency is decreased to once every 3 months, the cycle length will be 84 days. Dosing can also be interrupted until relapse and restarted, in such patients, per physician discretion. In the case of interruption, a cycle will be 3 months while treatment is held and the patient will restart at the dose level/schedule they were receiving at the time of interruption.

NOTE: As of Addendum 3, Arms A, B, and C are permanently closed to accrual. The 11 patients slotted to be enrolled in Arm C will now be treated with either the Arm A (if spliceosome-mutated/with ring sideroblasts) or Arm B (if spliceosome unmuted) treatment schedule.

7.1.1.4. Arms E and G Treatment Schedule

(Arms E and G permanently closed to accrual)

Induction Cycle 1 and 2 Dosing				
Agent	Dose	Route	Day	Cycle (ReRx) ± 3 days
Imetelstat	7.5 mg/kg	IV as 2 hour infusion	1	Cycle is 28 days
Maintenance: Cycles 3 and beyond ¹				

¹ Patients may continue to receive imetelstat study treatment for as long as they derive clinical benefit or until study end. The study will end when all subjects have discontinued study drug, the last patient enrolled has been treated for 5 years, or imetelstat is commercially available in the United States, whichever occurs first.

If any **one** of the following criteria is met at the end of Cycle 2, then follow the [Table 5](#) dosing schedule below. If no criteria are met, follow the instructions below.

- Greater than 75% reduction in leukocyte count
- Greater than 75% reduction in platelet count
- Greater than 50% reduction in spleen size in patients with baseline palpable splenomegaly of >5 cm
- Greater than 2 gm/dL increase in hemoglobin level from baseline without transfusions

Table 5: Arms E and G Dosing if Criteria met = Yes

Agent	Dose	Route	Day	Cycle (ReRx) ± 3 days
Imetelstat	7.5 mg/kg	IV as 2 hour infusion	1 ^{1,2}	Cycle is 28 days

¹ In patients who do not achieve CR or PR by the end of Cycle 4, the frequency of dosing may be increased to every week or every two weeks, at the physician's discretion

² For patients whose response has plateaued, without signs of further improvement, for a minimum of 3 months, dosing frequency may be reduced to every 2 to 3 months, or treatment may be interrupted until relapse and restarted, at the physician's discretion. In the case of interruption, a cycle will be 3 months while treatment is held and the patient will restart at the dose level/schedule they were receiving at the time of interruption.

Criteria met = No

Treat as specified in Arm F (Cycle 3 will start with Cycle 1 of Arm F dosing schedule)

7.1.1.5. Arm F Treatment Schedule

(Arm F permanently closed to accrual)

Induction Cycle 1 and 2 Dosing				
Agent	Dose	Route	Day	Cycle (ReRx) ± 3 days
Imetelstat	9.4 mg/kg	IV as 2 hour infusion	1	Cycle is 28 days
Maintenance: Cycles 3 and beyond¹				

¹ Patients may continue to receive imetelstat study treatment for as long as they derive clinical benefit or until study end. The study will end when all subjects have discontinued study drug, the last patient enrolled has been treated for 5 years, or imetelstat is commercially available in the United States, whichever occurs first.

If any **one** of the following criteria is met at the end of Cycle 2, then follow the [Table 6](#) dosing schedule below. If no criteria are met, follow the [Table 7](#) and [Table 8](#) dosing schedule below.

- Greater than 75% reduction in leukocyte count
- Greater than 75% reduction in platelet count
- Greater than 50% reduction in spleen size in patients with baseline palpable splenomegaly of >5 cm
- Greater than 2 gm/dL increase in hemoglobin level from baseline without transfusions

Table 6: Arm F Dosing if Criteria met = Yes

Agent	Dose	Route	Day	Cycle (ReRx) ± 3 days
Imetelstat	9.4 mg/kg	IV as 2 hour infusion	1	Cycle is 28 days

Table 7: Arm F Dosing if Criteria met = No: Cycles 3 and 4

Agent	Dose	Route	Day	Cycle (ReRx) ± 3 days
Imetelstat	7.5 mg/kg	IV as 2 hour infusion	1 and 3 ^{1,2}	Cycle is 28 days

¹ In patients who do not achieve CR or PR by the end of Cycle 4, the frequency of dosing may be increased to every two weeks, at physician's discretion.

² For patients whose response has plateaued, without signs of further improvement, for a minimum of 3 months, dosing frequency may be reduced to Day 1 every 28 days or Days 1, 3 every 2 to 3 months, or treatment may be interrupted until relapse and restarted, all at the physician's discretion. In the case of interruption, a cycle will be 3 months while treatment is held and the patient will restart at the dose level/schedule they were receiving at the time of interruption.

Table 8: Criteria met = No: Cycles 5 and beyond

Agent	Dose	Route	Day	Cycle (ReRx) ± 3 days
Imetelstat	7.5 mg/kg	IV as 2 hour infusion	1, 3, and 5 ^{1,2}	Cycle is 28 days

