¹ Cycle length = 28 days. For all patients who did not experience a treatment emergent abnormality in liver function tests (LFTs), defined as any grade abnormality in patients with normal value at baseline or any higher grade shift from baseline in patients with an abnormal baseline, or value more than 2x baseline if baseline was Grade ≥ 3 , or hepatic adverse events are present at imetelstat discontinuation, obtain LFT follow-up until 30 days from the last imetelstat dose. The length of the last cycle will be until 30 days after the last dose. For patients who experienced a treatment emergent abnormality in LFTs, as defined above, or hepatic adverse events are present at imetelstat discontinuation, obtain follow-up per test schedule (see Section 4 for details) until resolution to at least baseline grade or less than 2x baseline value if baseline was Grade ≥ 3 for at least 2 consecutive determinations. The length of the last cycle will be until the resolution is confirmed.

² In patients who do not achieve CR or PR, by the end of Cycle 4, the frequency of dosing may be increased to every two weeks, at the physician's discretion.

- ³ For patients whose response has plateaued, without signs of further improvement, for a minimum of 3 months, dosing may be reduced to Day 1 every 28 days or Days 1 and 3 every 2 to 3 months or treatment may be interrupted until relapse then restarted, all at the physician's discretion.
- ⁴ Patients may continue to receive imetelstat study treatment for as long as they derive clinical benefit or until study end. The study will end when all subjects have discontinued study drug, the last patient enrolled has been treated for 5 years, or imetelstat is commercially available in the United States, whichever occurs first.
- ⁵ Except relapse that occurs during dose interruption. These patients may restart treatment at the physician's discretion per Section 7.1.
- ⁶ If criteria still not met after Cycles 3 and 4, at the physician's discretion, dosing might be increased to Days 1, 3, and 5 every 28 days.

Figure 6: Schema – Arm G

(Note: Arm G permanently closed to accrual) (MDS/MPN or MDS patients with spliceosome mutations or ring sideroblasts)

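### Arm F, no criterion met: Section 7.1.1.5 and Table 8 set Days 1, 3 and 5 dosing from Cycle 5, while Figure 5 footnote 6 makes it conditional and discretionary (22.5 versus 15 mg/kg per 28 days)

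*Protocol*

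**What the plan says.** **Protocol Section 7.1.1.5 (Arm F).** Cycles 1 and 2 are 9.4 mg/kg on Day 1 of a 28-day cycle. Four criteria (leukocyte count, platelet count, spleen size, hemoglobin) are read at the end of Cycle 2. Patients who meet any one go to Table 6. For the others the instruction is: "If no criteria are met, follow the [Table 7](#) and [Table 8](#) dosing schedule below".

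- "Table 7: Arm F Dosing if Criteria met = No: Cycles 3 and 4" gives 7.5 mg/kg on Days 1 and 3.
- Table 8, "Criteria met = No: Cycles 5 and beyond", gives 7.5 mg/kg on Days 1, 3 and 5.
- The footnotes under Table 7, whose numbers Table 8 reuses, allow a move to two-weekly dosing for patients without CR or PR by the end of Cycle 4, and reduction or interruption after a plateau. Neither mentions the Day 5 infusion.

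**Protocol Figure 5 (Arm F schema), footnote 6.** If the criteria remain unmet after Cycles 3 and 4, then at the physician's discretion "dosing might be increased to Days 1, 3, and 5 every 28 days".

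**Protocol Section 7.1.1.4 (Arms E and G).** Patients who meet no criterion at the end of Cycle 2 are treated as in Arm F: "Cycle 3 will start with Cycle 1 of Arm F dosing schedule".

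**The concern.** A site treating an Arm F patient who met no criterion has two instructions for Cycle 5. The treatment section reads as a fixed sequence, Table 7 and then Table 8. The schema footnote describes an option that needs both a further look at the criteria and a physician's decision. A patient kept on Days 1 and 3 in Cycle 5 complies with the footnote but departs from Table 8 as written.

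A second ambiguity follows. Section 7.1.1.5 states a criteria check only at the end of Cycle 2, whereas footnote 6 presupposes another after Cycles 3 and 4. It is therefore unclear whether a patient who first meets a criterion in Cycle 3 or 4 should move to Table 8.

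Three things depend on this: how much drug a patient receives, whether a given dosing record counts as a deviation, and which regimen the arm's response and toxicity rates describe. The Arm E and F decision rule in Section 16.1 passes judgement on a regimen. SAP Section 4.2.2 reports response by arm, Section 3.3 lists exposure without summarising it, and Section 3.4 lists major deviations by cycle. The deviation listing needs one defined schedule to be measured against.

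**Working it through.** **1. Passages side by side, Arm F patient with no criterion met at the end of Cycle 2**

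| Question | Section 7.1.1.5 and Table 8 | Figure 5 footnote 6 |
|---|---|---|
| Is Days 1, 3, 5 automatic from Cycle 5? | Directed; no discretion stated | Discretionary |
| Are the criteria read again after Cycle 4? | Not stated; the only stated check is at the end of Cycle 2 | Yes, by implication |
| Criterion first met in Cycle 3 or 4 | Unclear | Step not available |
| Criterion still not met | Days 1, 3, 5 | Days 1, 3, 5 or no change |

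**2. Drug per 28-day cycle.** The plan states no per-cycle total, so there is no figure to reproduce. Inputs: 7.5 mg/kg per infusion and the infusion days, from Tables 7 and 8. Footnote 6 gives days but no dose; 7.5 mg/kg is assumed there too.

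- Days 1 and 3: 2 × 7.5 = 15.0 mg/kg.
- Days 1, 3 and 5: 3 × 7.5 = 22.5 mg/kg.
- Difference: 7.5 mg/kg; 22.5 / 15.0 − 1 = +50%.

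**3. Over the nine-cycle core phase**, with no hold, reduction or other frequency change.

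Arm F (Cycles 1–2 at 9.4 mg/kg once per cycle, Cycles 3–4 per Table 7, then Cycles 5–9):

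- Days 1 and 3 throughout Cycles 5–9: 2 × 9.4 + 2 × 15 + 5 × 15 = 123.8 mg/kg.
- Days 1, 3 and 5: 2 × 9.4 + 2 × 15 + 5 × 22.5 = 161.3 mg/kg.
- Difference: 37.5 mg/kg; 161.3 / 123.8 − 1 = +30%.

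Arm E or G patient moved to the Arm F schedule. Own Cycle 3 is Arm F Cycle 1, so own cycle = Arm F cycle + 2, and Arm F Cycle 5 is own Cycle 7:

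- Days 1 and 3 in own Cycles 7–9: 2 × 7.5 + 2 × 9.4 + 2 × 15 + 3 × 15 = 108.8 mg/kg.
- Days 1, 3 and 5: 2 × 7.5 + 2 × 9.4 + 2 × 15 + 3 × 22.5 = 131.3 mg/kg.
- Difference: 22.5 mg/kg; 131.3 / 108.8 − 1 = +21%.

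**4. Effect on the stated design.** The Arm E and F rule (5 or more successes in 25) gives 0.098, 0.318, 0.579, 0.786 and 0.910 at true rates of 0.10 to 0.30. This agrees with the Section 16.1 table (0.10, 0.32, 0.58, 0.79, 0.91). The dosing conflict does not alter these figures.

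**5. Timing.** Accrual closed on 22 January 2014, and treatment had to start within 7 days of registration. Arm F Cycle 5 begins after 4 × 28 = 112 days, so without holds the last patient would reach it about 119 days after closure, in May 2014. Own Cycle 7 for Arms E and G begins after 6 × 28 = 168 days, so at latest about 175 days after closure, in July 2014. Both precede Amendment 13 (5 October 2015).

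**The case against.** **Table 8's heading is itself conditional.** It can be read as applying only to patients who still meet no criterion at Cycle 5, and Section 8.1 has efficacy evaluated at the end of every cycle. This stands. A reader might infer that Section 7.1.1.5 definitely escalates patients without any re-check, but the text does not settle that. On the conditional reading the difference over re-checking disappears; automatic versus discretionary remains.

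**The two-weekly option.** A reader might count Table 7 footnote 1 ("the frequency of dosing may be increased to every two weeks") as a third conflicting instruction. It is not: Figure 5 footnote 2 gives the same option on the same trigger.

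**Responders being escalated.** It is also tempting to say that responders would be escalated. The switch depends on the four criteria, not on IWG-MRT response, which requires benefit for at least 12 weeks. Cycles 3 and 4 together last 8 weeks.

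**Discretion is everywhere.** Every arm allows discretionary frequency changes, so the arm would mix schedules even after reconciliation. This stands too: the conflict does not by itself invalidate the endpoint, decision rule or power. It does leave the intended schedule undefined.

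**Limits of the text.** The Figure 5 diagram and the SAP's Arm F schedule figure are not shown, and no footnote text appears beneath Table 8. A qualifier there could narrow the conflict. The point rests on footnote 6 and the directive sentence, which are both legible.

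**Little left to change.** The Cycle 5 decision was past for nearly everyone by Amendment 13, and SAP Section 3.3 lists dose received, adjustments and reasons. This limits the practical effect. However, Table 8 governs all later cycles, and patients deriving benefit may continue treatment.

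**Conclusion.** The contradiction is real. One passage sets Days 1, 3 and 5 from Cycle 5 for Arm F patients who met no criterion at the end of Cycle 2. The other makes it a physician's option that depends on the criteria still being unmet after Cycles 3 and 4. The size is 22.5 versus 15 mg/kg per 28-day cycle (+50%) for a patient who would otherwise stay on Days 1 and 3, or +30% over nine core cycles.

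Arm E and G patients transferred to this schedule inherit the conflict on the Arm F cycle count, so at the earliest in their own Cycle 7 (+21% over nine cycles). If the Arm F schedule is followed literally, they reach Tables 7 and 8 only after failing the criteria again at the end of Arm F Cycle 2.

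These figures assume 7.5 mg/kg per infusion under both passages and no hold, reduction or other frequency change. They also assume that Table 8 reuses Table 7's footnotes. With accrual closed, the main consequence is for how exposure, deviations and the tested regimen are interpreted. Nothing here indicates which schedule is right.

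**What to change.** Reconcile Section 7.1.1.5 and Table 8 with Figure 5 footnote 6. The wording should state:

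- whether the step to Days 1, 3 and 5 is automatic or discretionary;
- whether the criteria are read again after Cycle 4, and what follows if one is first met in Cycle 3 or 4;
- which cycle count applies to Arm E and G patients on the Arm F schedule.

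The choice on each is the sponsor's. The two-weekly option needs no change. The cost is protocol wording only, with no effect on sample size or the decision rule. The study report should say which reading was used when exposure and deviations were assessed.
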